16.0 Statistical Considerations and Methodology

16.1 Overview: This protocol will assess the efficacy of maintenance auranofin plus sirolimus after at least one line of platinum based chemotherapy for lung cancer (squamous, Ras-mutated adenocarcinoma, or small cell lung cancer) patients with no acceptable standard treatment options, using a one-stage phase II study design. A run-in phase I study (described in Section 7.0) will be conducted to determine the MTD for the phase II portion.

16.11 Phase I Study

This run-in phase I study is a cohorts of 3 design. For a subject to be considered evaluable for dose-limiting toxicity (DLT) the subject must have received at least one dose of each drug in Cycle 1. If a subject withdraws from the study within the first cycle of treatment for reasons other than adverse events, the subject will be replaced; and only DLTs occurring in Cycle 1 will be used for establishing safety during the run-in phase I study. However, all adverse event data will be summarized in the final analysis. For this run-in phase I study, DLT the study design is defined in Section 7.0. The patients treated at the MTD within the phase I will be included in the phase II efficacy analysis. Safety for all patients (including the patients in the run-in phase I study) will continue to be monitored via the Adverse Event Stopping Rule.

- 16.12 Sample Size: Phase I: The study may involve a maximum of 12 patients (6 for each of 2 dose levels). Phase II: This study will accrue an additional 35 patients to have a total of 41 patients accrued to the efficacy portion of this study (6 patients at the MTD in the phase I portion plus 35 patients accrued during the phase II portion). This includes 10% overaccrual of patients during the phase II portion to allow for cancellation, ineligibility, and major treatment violations (i.e., accrual of 41 patients to have 37 evaluable patients as required in 16.41). Overall: Therefore, overall, the study will accrue a maximum of 47 patients.
- 16.13 Accrual Time and Study Duration: The anticipated accrual rate is approximately 2 patients per month, based on physician estimate. This corresponds to a requirement of approximately 17 weeks to enroll (12 weeks), treat (4 weeks), and evaluate (1 week to submit data) 6 patients. Therefore, the accrual time for the phase I portion will be a maximum of 34 weeks. The overall study duration will be 34 weeks (phase I component) + 70 weeks (accrual of an additional 35 patients) + 16 weeks (4 months to evaluate the primary endpoint) = 120 weeks (about 28 months). The final analysis can begin approximately 28 months after activation, i.e., as soon as the last patient has been observed for 4 months and data have been submitted.

16.14 Operating Characteristics: The following table gives the probability of dose escalation at a single dose level as a function of the true probability of DLT at that level using the cohorts of 3 design described in Section 7.0.

| True Rate of DLT (%) | Probability of Dose Escalation |
|----------------------|--------------------------------|
| 10 | 0.91 |
| 20 | 0.71 |
| 30 | 0.49 |
| 40 | 0.31 |
| 50 | 0.17 |

16.2 Phase I Analysis Plans: All the relevant phase I results pertaining to adverse events, MTD, clinical endpoints, and laboratory correlates will be examined in an exploratory and hypothesis generating fashion.

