7.0 Protocol Treatment

7.1 Treatment Schedule

7.11 Phase I Cohort:

| Agent | Dose Level | Route | Day | ReRx |
|-----------|---------------------|-------|-----------------------------------|------|
| Auranofin | As assigned by | PO | PO Daily | |
| | Registration office | | | days |
| Sirolimus | 5 mg | PO | Daily (cycle 1 only, begin day 8, | Q28 |
| | | | subsequent cycles begin day 1) | days |

7.12 Phase 2 Cohort (at MTD from Phase I):

| Agent | Dose Level | Route | Day | ReRx |
|-----------|--------------------|-------|-----------------------------------|------|
| Auranofin | As determined by | PO | Daily | Q28 |
| | studies in Phase I | | | |
| Sirolimus | olimus 5 mg PO | | Daily (cycle 1 only, begin day 8, | Q28 |
| | | | subsequent cycles begin day 1) | days |

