7.2 Phase I Dose Escalation and Determination of MTD

7.21 Dose Escalation Guidelines

| Dose Level | Auranofin |
|------------|------------|
| 0* | 3 mg daily |
| 1 | 6 mg daily |

^{*} Starting dose level.

- 7.211 Three patients will be treated at each dose level and observed for a minimum of 1 cycle, to assess toxicities, before new patients are treated.
- 7.212 Investigators are to contact the Study Chair as soon as any dose-limiting toxicity occurs.
- 7.213 For this protocol, dose-limiting toxicity (DLT) will be defined as an adverse event attributed (definitely, probably, possibly) in the first cycle to the study treatment and meeting the following criteria:

| Toxicity | DLT Definition |
|-------------|--------------------------|
| Hematologic | Grade 4 Neutropenia |
| | Grade 4 Thrombocytopenia |
| Non- | ≥Grade 3 Anaphylaxis |
| hematologic | |
| | ≥Grade 3 Proteinuria |
| | |
| | ≥Grade 3 Hematuria |
| | ≥Grade 3 Rash acneiform |
| | ≥Grade 3 Diarrhea |
| | ≥Grade 3 Mucositis oral |

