7.22 MTD Determination

MTD is defined as the dose level below the lowest dose that induces doselimiting toxicity in at least one-third of patients (at least 2 of a maximum of 6 new patients).

7.221 Three patients will be treated at a given dose level combination and observed for at least 1 cycle to assess toxicity (accrual will be suspended while the 3 patients are treated and observed).

- 7.222 If dose-limiting toxicity (DLT) is not seen in any of the 3 patients, 3 new patients will be accrued and treated at the next higher dose level. If DLT is seen in 2 or 3 of 3 patients treated at a given dose level, then the next 3 patients will be treated at the next lower dose level, if only 3 patients were enrolled and treated at this lower dose level.
- 7.223 If DLT is seen in 1 of 3 patients treated at a given dose level, up to 3 additional patients will be enrolled and treated at the same dose level (accrual will be suspended while the 3 patients are treated and observed). If DLT is seen in at least one of these additional three patients (≥2 of 6), the MTD will have been exceeded and further accrual will cease to this cohort. If DLT is not seen in any of the three additional patients, 3 new patients will be accrued and treated at the next higher dose level.
- 7.224 After enrolling 6 patients on a specific dose level, if DLT is observed in at least 2 of 6 patients, then the MTD will have been exceeded and defined as the previous dose unless only 3 patients were treated at the lower dose level. In that case, 3 additional patients will be treated at this lower dose level.
- 7.23 Dose Escalation: Doses will not be escalated in any individual patient.
- 7.24 If a patient fails to complete Cycle 1 for reasons other than toxicity, the patient will be regarded as treatment intolerant and an additional patient will be treated at the current dose level.
- 7.3 Patients can be instructed in administration techniques for both sirolimus and auranofin and granted treatment independence.
- 7.4 Patient must return to Mayo Clinic for evaluation at least every week during the first cycle of treatment and then at least every 4 weeks.
- 7.5 Study treatment by a local medical doctor (LMD) is not allowed.

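### Section 16.11 requires a dose of both drugs for DLT evaluability, but sirolimus starts on day 8, so an auranofin-only DLT that prevents sirolimus counts in Section 7 yet is not evaluable in 16.11

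*Combined protocol and SAP*

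**What the plan says.** - **Evaluability (16.11).** To be evaluable for DLT, "the subject must have received at least one dose of each drug in Cycle 1". No exception is made for a patient who has already had a DLT.
- **Schedule (7.11).** Auranofin is daily. The sirolimus entry reads "Daily (cycle 1 only, begin day 8", so days 1-7 of cycle 1 are auranofin alone. Only auranofin is escalated (7.21).
- **DLT definition (7.213).** A DLT is a listed event that is an "adverse event attributed (definitely, probably, possibly) in the first cycle to the study treatment". Exposure to both drugs is not required.
- **Escalation rules (7.222-7.224).** DLTs are counted among patients treated, in groups of 3 or 6. For example: "If dose-limiting toxicity (DLT) is not seen in any of the 3 patients, 3 new patients will be accrued" at the next level.
- **Replacement.** Section 16.11 covers a patient who withdraws in cycle 1: "for reasons other than adverse events, the subject will be replaced". Section 7.24 adds a patient in a similar case: "If a patient fails to complete Cycle 1 for reasons other than toxicity, the patient will be regarded as treatment intolerant".
- **Link between the sections.** Section 16.11 also states: "For this run-in phase I study, DLT the study design is defined in Section 7.0".

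**The concern.** Sections 16.11 and 7 give different answers for the same patient. Take a patient with a listed, attributed DLT on days 1-7 who then receives no sirolimus in cycle 1. Section 7 counts that DLT. Section 16.11 makes the patient non-evaluable, and neither replacement rule applies because the exit was for toxicity.

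At stake is an escalation decision made on 3 or 6 patients. On the literal reading a DLT on the escalated drug is left out of that decision, and the cohort is left at a size for which the rules are not written. The patients concerned would be those with the most serious early events.

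**Working it through.** **1. The plan's own figure.** Under 7.222-7.223 a level is passed with 0 DLTs in 3 patients, or with 1 in 3 followed by 0 in 3 more. With true DLT rate p:

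P(escalate) = (1-p)^3 + 3p(1-p)^2 × (1-p)^3 = (1-p)^3 + 3p(1-p)^5

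| p | Computed | Table in 16.14 |
|---|---|---|
| 0.10 | 0.906 | 0.91 |
| 0.20 | 0.709 | 0.71 |
| 0.30 | 0.494 | 0.49 |
| 0.40 | 0.309 | 0.31 |
| 0.50 | 0.172 | 0.17 |

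The table is correct for the Section 7 design, with every DLT in every treated patient counted. It has no term for a non-evaluable patient, so it does not settle how 16.11 is to be read.

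**2. One patient traced through the rules.** A listed, attributed DLT occurs on days 1-7 and no sirolimus follows in cycle 1.

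| Rule | Result |
|---|---|
| 7.213 | DLT |
| 7.222-7.224 | Counted; the patient was treated |
| 16.11, evaluability | Not evaluable; only one drug taken |
| 16.11, replacement | Not replaced; the exit was for an adverse event |
| 7.24 | No additional patient; the reason was toxicity |

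**3. Effect on the count, read literally.** The patient leaves both numerator and denominator:

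- First cohort: 1/3 becomes (1-1)/(3-1) = 0/2.
- Expanded cohort: 2/6 becomes (2-1)/(6-1) = 1/5.

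Sections 7.222-7.224 give outcomes for 3 and for 6 patients. They give no next step for 2 or 5.

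**4. How narrow the case is.** The 7.213 events at grade 3-4 fall in rows of table 8.2 that delay therapy first and stop it only if toxicity lasts beyond 14 days. The latest auranofin-only day is day 7, and 7 + 14 = day 21 of a 28-day cycle. A patient who recovers within that delay can still take sirolimus in cycle 1 and become evaluable. What remains is mainly DLTs that do not resolve, withdrawals for toxicity, and deaths.

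**5. How often a cohort would meet the conflict.** Let w be the share of DLTs that occur on days 1-7 and prevent any cycle-1 sirolimus. The documents give no value, so w is assumed to lie between 0 and 10%. With independent patients, P(at least one such patient in a first cohort of 3) = 1 - (1 - pw)^3.

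| p | w = 0 | w = 5% | w = 10% |
|---|---|---|---|
| 0.10 | 0 | 0.015 | 0.030 |
| 0.20 | 0 | 0.030 | 0.059 |
| 0.30 | 0 | 0.044 | 0.087 |
| 0.40 | 0 | 0.059 | 0.115 |
| 0.50 | 0 | 0.073 | 0.143 |

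For example, at p = 0.30 and w = 10%: 1 - (1 - 0.03)^3 = 1 - 0.97^3 = 0.087.

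**The case against.** The strongest reply is that the operating rules already count the event. Section 7.2 decides escalation on patients treated and does not use evaluability as a filter. Section 16.11 defers to Section 7.0 for the design and uses DLTs occurring in cycle 1, which includes days 1-7. Both replacement rules leave out toxicity exits, which makes sense only if those patients count. Section 7.212 says: "Investigators are to contact the Study Chair as soon as any dose-limiting toxicity occurs". Accrual is also suspended while each cohort is observed (7.221), so a cohort left at two would be noticed. All of this stands as evidence of intent. It does not remove the conflict: Section 7 never defines DLT evaluability, the deferral sentence as it reads is unclear, and nothing sets aside the condition in 16.11.

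The reply that w may be close to zero also stands. Besides the 14-day delay, section 15.15 gives auranofin a blood half-life of 21-31 days. Assuming simple first-order accumulation, day-7 blood gold is 1 - 2^(-7/31) = 0.14 to 1 - 2^(-7/21) = 0.21 of steady state, which argues against early cumulative toxicity. Acute events remain possible: anaphylaxis of grade 3 or more is a listed DLT.

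A reader might go further and infer that 16.11 turns 1/3 into 0/3, or 2/6 into 1/6, and so raises the probability of escalation above the 16.14 values. The documents do not support that. It would require refilling the slot, which neither replacement rule provides for this patient, or scoring a non-evaluable patient as free of DLT, which no passage says. The literal result is an undefined next step, and no escalation probability can be attached to it.

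**Conclusion.** The conflict is real and minor. Section 16.11 and Section 7 disagree on a patient whose DLT on days 1-7 prevents any cycle-1 sirolimus, and the literal reading leaves 0/2 or 1/5 with no rule to apply. The probable intent is to count the event, but that is inference.

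At a true DLT rate of 30%, a first cohort of 3 would meet the conflict with probability 0-9%. This rests on the assumed w of 0-10% and on independence between patients; the lower end is credible given the 14-day delay. The run-in has at most 12 patients and two dose levels, so one escalation step is involved, plus the count at the higher level. It deserves correction because it touches a safety decision, not because it is likely to occur. Nothing here shows the 16.14 table to be wrong.

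**What to change.** Reconcile the evaluability sentence in 16.11 with 7.213, 7.222-7.224 and 7.24, so that:

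1. the both-drugs condition applies only to patients without a DLT;
2. a cycle-1 DLT, as 7.213 already defines it, counts whether or not sirolimus had started;
3. every treated patient is either counted or replaced.

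The cost is one sentence in 16.11 and matching wording in 7.24. Counting these DLTs adds no patients, visits or data, and leaves the DLT list, the doses and the 16.14 table unchanged. The downside is a slightly higher chance of not escalating than if such events were left out.

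### Section 16.12 fixes phase II accrual at 35 and reaches 41 only if 6 phase I patients were treated at the dose carried forward, which Section 7.2 does not assure after 0/3 DLT at the top level

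*Combined protocol and SAP*

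**What the plan says.** **Sample size (16.12).** For phase I: "The study may involve a maximum of 12 patients (6 for each of 2 dose levels"), so 6 per level is an upper bound. For phase II the section adds a fixed 35 patients and counts "6 patients at the MTD in the phase I portion plus 35 patients accrued during the phase II portion". It explains the total as "accrual of 41 patients to have 37 evaluable patients as required in 16.41". The overall cap is 47. Section 16.11 brings the phase I patients treated at the MTD into the phase II efficacy analysis. Section 16.13 allows 70 weeks for the 35.

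**Escalation (7.2).** Cohorts are of 3. The outcomes are:
- 0/3 DLT: "3 new patients will be accrued and treated at the next higher dose level" (7.222).
- 1/3 DLT: "up to 3 additional patients will be enrolled and treated at the same dose level" (7.223).
- A level exceeded while the one below it has only 3 patients: 3 more are treated at that lower level (7.222, 7.224).
- A patient who leaves Cycle 1 for reasons other than toxicity: "an additional patient will be treated at the current dose level" (7.24).

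Phase I has two levels, 0 and 1 (7.21, 12.3). The definition in 7.22 is "MTD is defined as the dose level below the lowest dose that induces doselimiting toxicity in at least one-third of patients", and 7.12 doses phase II at the MTD.

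**Decision rule (16.41).** The regimen is taken forward on 17 or more successes in the first 37 evaluable patients. No cut-off is given for fewer than 37.

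**The concern.** Section 16.12 treats as given a count that Section 7.2 produces only on some paths. After 0/3 DLT at level 1 the only instruction is to go to a higher level, and none exists. No rule expands level 1 to 6. No passage makes the 35 depend on how many phase I patients were treated at the dose carried forward.

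This is the favourable path, on which the combination is well tolerated at the top level. If phase II then stops at 35, the study falls short of the number that 16.12 itself says it needs for 37 evaluable. What is at stake is the allowance for cancellation, ineligibility and major violations, and with it a little power.

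**Working it through.** **1. The plan's own figures.** 6 + 35 = 41 and 12 + 35 = 47. An allowance of 10% on 37 gives 37 × 1.10 = 40.7, rounded up to 41. For X ~ Bin(37, p), P(X ≥ 17) is 0.112 at p = 0.35 and 0.898 at p = 0.55, against 0.11 and 0.90 in 16.42. The chance of clearing a level, (1−p)³ + 3p(1−p)⁵, is 0.906, 0.709 and 0.494 at p = 0.1, 0.2 and 0.3, against 0.91, 0.71 and 0.49 in 16.14. All of these reproduce.

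**2. Patients at the dose carried forward, by path (no replacements under 7.24).**

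| Path | At that dose | Plus 35 |
|---|---|---|
| Level 1 clears as 1/3 then 0/3 | 6 | 41 |
| Level 1 exceeded, level 0 confirmed | 6 | 41 |
| Level 1 shows 0/3 and is left at 3 | 3 | 38 |

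The margin over 37 is 41 − 37 = 4 on the first two paths and 38 − 37 = 1 on the third.

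**3. Chance of the third path.** The formula is [(1−p₀)³ + 3p₀(1−p₀)⁵] × (1−p₁)³, with assumed true DLT rates p₀ at level 0 and p₁ at level 1.

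| p₀, p₁ | Calculation | Probability |
|---|---|---|
| 10%, 10% | 0.906 × 0.729 | 0.66 |
| 10%, 20% | 0.906 × 0.512 | 0.46 |
| 10%, 30% | 0.906 × 0.343 | 0.31 |
| 20%, 30% | 0.709 × 0.343 | 0.24 |

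**4. Effect of 38 in place of 41.** Let each accrued patient be evaluable independently with probability 1 − loss. The loss rates are assumptions; the 10% in 16.12 is an allowance, not a known rate. The number evaluable is n ~ Bin(accrued, 1 − loss), capped at 37. For each n, take the smallest cut-off c with P(X ≥ c | 0.35) ≤ 0.12, then average P(X ≥ c | 0.55) over n. Re-choosing c for each n is a device of this check and is not in 16.41. Cut-off, alpha and power by n:
- n = 34: 16, 0.099, 0.865
- n = 35: 17, 0.068, 0.825
- n = 36: 17, 0.088, 0.865
- n = 37: 17, 0.112, 0.898

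| Assumed loss | P(≥37 evaluable), 38 accrued | P(≥37 evaluable), 41 accrued | Average power, 38 | Average power, 41 | Difference (points) |
|---|---|---|---|---|---|
| 10% | 0.10 | 0.61 | 0.8485 | 0.8791 | 3.1 |
| 5% | 0.43 | 0.95 | 0.8709 | 0.8958 | 2.5 |
| 2% | 0.82 | 1.00 | 0.8909 | 0.8980 | 0.7 |
| 1% | 0.94 | 1.00 | 0.8960 | 0.8981 | 0.2 |

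If loss falls only on the 35 phase II patients, average power is 0.851 against 0.885 at 10% and 0.873 against 0.897 at 5%, which is much the same.

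**The case against.** The gap can be placed in Section 7.2 instead of 16.12. Section 7.2 does not say that level 1 stops at 3 after 0/3; it says nothing. Section 16.12 speaks of 6 at the MTD and 16.13 times phase I in sixes, so 16.12 might be read as supplying the missing number. Moreover, a wholly literal reading of 7.22 gives no MTD on this path, and 16.11 carries forward only patients treated at the MTD. The figure of 3 carried patients is then not fixed by the text either. This stands: 38 is one reading, not a number the documents determine. But 16.12 also calls 6 per level a maximum, and if 6 is meant, 7.2 lacks the rule that delivers it. The passages need reconciling on either reading.

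It can also be said that 41 and 37 are the governing numbers and accrual would simply continue to 41. The cap of 47 leaves room, and no passage makes 35 a ceiling. That may be the intent, but only 35 is written, and 16.13 times phase II on it.

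A reader might infer more: that the phase II test is underpowered, with power near 0.78. That figure (0.776, with alpha 0.051) needs 34 evaluable and an unchanged cut-off of 17. The expected number at 10% loss is indeed 38 × 0.9 = 34.2, but 16.41 does not say that 17 would be kept below 37. The missing cut-off is also not peculiar to this path: with 41 accrued and 10% loss, fewer than 37 are evaluable with probability 1 − 0.61 = 0.39.

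**Conclusion.** The inconsistency holds, conditionally, and is minor. The 41 in 16.12 depends on 6 phase I patients at the dose carried forward, and Section 7.2 does not secure that number when level 1 shows 0/3 DLT. The shortfall of 3 patients arises only if level 1 stays at 3, no replacements are added, and accrual stops at 35.

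The sum 6 + 35 is right, the 37-patient design reproduces, and 38 still exceeds 37. The documents therefore do not support reading this as a failed design or a wrong decision rule. The cost in average power is about 0.2 to 3.1 points over assumed losses of 1% to 10%, and the upper end holds only at 10%. The path is not remote, at 0.24 to 0.66 over the DLT rates tried, but those rates are assumptions too.

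**What to change.** In 16.12, state 41 as the accrual target for the efficacy portion and replace the fixed 35 by *41 minus the number of phase I patients treated at the dose carried into phase II*. That is 35 if there are 6 and 38 if there are 3.

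In 16.13, make the accrual term follow that number: 35 × 2 = 70 weeks or 38 × 2 = 76 weeks. The 34-week phase I term covers 6 patients at both levels, so it should be matched to the path as well; 6 weeks should not simply be added to the printed 120.

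The sponsor should reconcile 7.12, 7.22 to 7.224 and 16.11 to 16.12 on what is carried forward, and with how many patients, when level 1 does not reach the DLT limit. That choice is the sponsor's. If it always yields 6, the formula returns 35 and nothing else changes.

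The cost is wording, plus up to 3 more phase II patients, or about 3 × 2 = 6 weeks of accrual. The study total without replacements is 3 + 3 + 38 = 44, or 6 + 3 + 38 = 47 if level 0 had been expanded. Both are within the cap of 47.

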16.21 Adverse Events Profile

The number and severity of all adverse events (overall and by dose level) will be tabulated and summarized.

16.22 Clinical Endpoints

Overall survival, progression-free survival, and response will be summarized descriptively (overall and by dose level).

16.3 Phase II Design and Analysis

16.31 Primary Endpoint: The primary endpoint of this trial is the 4-month progression-free survival rate. Throughout Section 16.0, "4-month progression-free survivor" will be considered synonymous with "success", unless otherwise specified. A patient is considered to be a 4-month progression-free survivor if the patient is 4 months from registration without a documentation of disease progression (note, the patient need not be on study treatment at 4 months to be considered a success). All patients meeting the eligibility criteria who have signed a consent form and have initiated treatment will be evaluable for the primary endpoint.

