4.0 Test Schedule

| | 1 | T | | 1 |
|--|------------------|------------------------|---------|------------------------|
| | ≤14 days | | | Prior to subsequent |
| | prior to | Weekly | | cycles |
| Tests and procedures | registration | $(\pm 2 \text{ days})$ | Cycle 1 | $(\pm 2 \text{ days})$ |
| History and exam, wt, PS | X | | X | X |
| Height | X | | | |
| Adverse event assessment | X | | | X |
| Tumor measurement (CT, PET/CT) | \mathbf{X}^{1} | | | X^2 |
| Hematology group WBC, ANC, Hgb, PLT | X | X^4 | X | X |
| Chemistry group Na, K, chloride, glucose, creatinine, total bilirubin, albumin, alkaline phosphatase, SGOT (AST), SGPT (ALT) | X | X ⁴ | X | X |
| Lipid Panel | XR | | | X8 |
| Urinalysis/urine protein dipstick | X | X^4 | X | X |
| Pregnancy Test | X ³ | | | |
| Patient Medication Diary for Sirolimus and Auranofin (Appendix II) ⁵ | | | X | X |
| Mandatory research tissue (see Section 17) ^{6,7} | X^R | | | |

- 1. Imaging studies such as chest x-ray, CT scans, and MRIs can be performed ≤30 days prior to registration. Use same imaging throughout the study. The CT portion of a PET CT can be considered interchangeable with a CT scan.
- 2. Tumor assessment must be performed at least every other cycle after completing Cycle

- 2;
- i.e. after Cycles 2, 4, 6, etc. Tumor assessment should be performed at any time during the treatment cycle that disease progression is clinically suspected so that patient can go off treatment and receive other therapy.
- 3. Women of childbearing potential only. Must be done \leq 7 days prior to registration.
- 4. Weekly during cycle 1 only.
- 5. The diary must begin the day the patient starts taking the medication and must be completed per protocol and returned to the treating institution OR compliance must be documented in the medical record by any member of the care team.
- 6. Tissue specimens must be collected and submitted *once at baseline*.
- 7. Optional repeat biopsy of accessible tumor at response and/or disease progression.
- 8. Lipid panel is performed at baseline, prior to cycle 2, every other cycle through cycle 6, and then as clinically indicated (per Standard of Care) thereafter.
- 9. R Research funded (see Section 19.0).

5.0 Grouping Factor:

5.1 Phase: Phase I vs Phase II.

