6.3 Phase I and II

6.31 Correlative Research

Mandatory

A mandatory correlative research component is part of this study, the patient will be automatically registered onto this component (see Sections 3.19c and 17.0).

Optional

An optional correlative research component is part of this study: there will be an option to select if the patient is to be registered onto this component (see Section 17.0).

- Patient has/has not given permission to give his/her *tissue* sample for research testing as a part of this study (see section 17.0).
- 6.32 Prior to accepting the registration, registration/randomization application will verify the following:
 - IRB approval at the registering institution
 - Patient eligibility
 - Existence of a signed consent form
 - Existence of a signed authorization for use and disclosure of protected health information
- 6.33 Documentation of IRB approval must be on file in the Registration Office before an investigator may register any patients.

In addition to submitting initial IRB approval documents, ongoing IRB approval documentation must be on file (no less than annually) at the Registration Office ([contact]). If the necessary documentation is

not submitted in advance of attempting patient registration, the registration will not be accepted and the patient may not be enrolled in the protocol until the situation is resolved.

When the study has been permanently closed to patient enrollment, submission of annual IRB approvals to the Registration Office is no longer necessary.

- 6.34 At the time of registration, the following will be recorded:
 - Patient has/has not given permission to store and use his/her sample(s) for future research of Non-small cell lung cancer at Mayo.
 - Patient has/has not given permission to store and use his/her sample(s) for future research to learn, prevent, or treat other health problems.
 - Patient has/has not given permission for MCCC to give his/her sample(s) to researchers at other institutions.
- 6.35 Treatment on this protocol must commence at Mayo Clinic Arizona institution under the supervision of a medical oncologist.
- 6.36 Treatment cannot begin prior to registration and must begin \Box 14 days after registration.
- 6.37 Pretreatment tests/procedures (see Section 4.0) must be completed within the guidelines specified on the test schedule.
- 6.38 All required baseline symptoms (see Section 10.3) must be documented and graded.

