8.2 Dose modification Table

| ☐ ☐ Use the NCI Common Terminology Criteria for Adverse Events (CTCAE) version | | | |
|--|---------------|-------|--------|
| 4.0* unless otherwise specified \square | | | |
| CTCAE System/Organ/ Class (SOC) | ADVERSE EVENT | AGENT | ACTION |
| BASED ON INTERVAL ADVERSE EVENT | | | |

| □ □ Use the N | CI Common Terminolog 4.0* unless o | | or Adverse Events (CTCAE) version |
|--|--|------------------------|---|
| CTCAE System/Organ/ Class (SOC) | ADVERSE EVENT | AGENT | ACTION |
| Investigations | Neutrophil count decreased Grade 4 Platelet count decreased Grade 4 | Auranofin Sirolimus | Delay therapy until ANC ≥ 1500 and/or PLT ≥ 100,000, and decrease by 1 dose level; discontinue treatment if toxicity persists beyond 14 days or if subject is already at dose level -2 and go to event monitoring phase per Section 18. |
| | Neutrophil count decreased Grade 3 Platelet count decreased Grade 3 | | Delay therapy until ANC ≥ 1500 and/or PLT ≥ 100,000. If delay is 1 week or less, resume at prior dose. If delay exceeds 7 days but is not more than 14 days, decrease by 1 dose level; discontinue treatment if toxicity persists beyond 14 days or if subject is already at dose level -2 and go to event monitoring phase per Section 18. |
| | Cholesterol High Grade 2 | | Institute appropriate lipid/cholesterol lowering therapy. Hold treatment until levels return to Grade 1. If unresolved by four weeks, discontinue auranofin and sirolimus therapy and go to event monitoring. |
| | Grade 3-4 | | Discontinue auranofin and sirolimus and go to event monitoring. |
| Respiratory, thoracic and mediastinal disorders | Interstitial pneumonitis any grade | Auranofin Sirolimus | Discontinue and go to event monitoring |

| \Box Use the NCI Common Terminology Criteria for Adverse Events (CTCAE) version 4.0* unless otherwise specified \Box \Box | | | |
|---|---------------------------------|------------------------|---|
| CTCAE System/Organ/ Class (SOC) | ADVERSE EVENT | AGENT | ACTION |
| Metabolism and nutrition disorders | Hypertriglyceridemia Grade 2 | Auranofin Sirolimus | Institute appropriate lipid/cholesterol lowering therapy. Hold treatment until levels return to Grade 1. If unresolved by four weeks, discontinue auranofin and sirolimus therapy and go to event monitoring. |
| | Grade 3-4 | | Discontinue auranofin and sirolimus and go to event monitoring. |

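### The 4-month success rule in 16.31 requires no scan and gives no day count, so progression first seen after the landmark, or never looked for, is scored as success

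*Combined protocol and SAP*

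**What the plan says.** Section 16.31 sets the primary endpoint: "A patient is considered to be a 4-month progression-free survivor if the patient is 4 months from registration without a documentation of disease progression". It adds that the patient need not still be on treatment. Evaluability requires eligibility, consent and started treatment, but no post-baseline scan. Four months is not given in days.

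The scan schedule runs on a different clock. Footnote 2 of Section 4.0 states "Tumor assessment must be performed at least every other cycle after completing Cycle" 2, that is, after cycles 2, 4 and 6, and the schema gives a 28-day cycle. Section 11.1 asks for re-evaluation every 8 weeks and does not say whether this continues off treatment. Section 6.36 says "Treatment cannot begin prior to registration and must begin" 14 days after registration; the comparison sign is lost in the text and is read here as at most. Section 8.2 allows holds that move later cycles, for example "If delay exceeds 7 days but is not more than 14 days", and up to four weeks for raised lipids.

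Section 16.52 dates progression at documentation and counts death as progression. Section 16.512 adds a Kaplan-Meier estimate only if patients are lost before 4 months. Under 13.3, patients who stop without PD go to event monitoring, for which Section 18.0 gives a form timetable (every 3 months until PD) and no imaging schedule.

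**The concern.** A yes/no endpoint at a fixed time needs an assessment attached to that time. Here absence of a record is enough. Two kinds of patient can be scored as successes although they have progressed: those whose second scan falls after the landmark and shows PD that gave no symptoms, and those who stopped treatment without PD and were not rescanned. Within this trial, such misclassification can only add to the success count.

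The decision rule leaves little room. At a true rate of 35%, wrongly counting one, two or three of the 37 patients as successes lowers the effective threshold from 17 to 16, 15 or 14, and the chance of a positive result rises from 0.11 to 0.19, 0.29 or 0.42.

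**Working it through.** **Printed design.** Inputs from 16.41 and 16.42: n = 37, positive if 17 or more successes, exact binomial. P(X ≥ 17) at 0.35, 0.40, 0.45, 0.50 and 0.55 is 0.112, 0.282, 0.518, 0.744 and 0.898. All five agree with the printed table (0.11, 0.28, 0.52, 0.74, 0.90).

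**Scan timing, in days from registration.** Second scan = start lag + 4 × 28 = lag + 112. A lag of 0 to 14 gives days 112 to 126. A 14-day hold makes this days 126 to 140. The ±2-day visit window is ignored. Four calendar months is 4 × 30.4375 = 121.75, about day 122. Without holds, the scan is late when the lag exceeds 10 days.

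**Size, as an illustration.** Assumptions not in the documents:
- PFS is exponential, with 35% as the true rate at landmark L, so S(t) = 0.35^(t/L).
- The start lag is uniform and there are no holds.
- A share d of progressions is counted at once (death, triggered scan or symptomatic deterioration). The rest are found only on scheduled scans.

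Among the rest, success is scored from the second scan if it falls by L, and otherwise from the first scan (lag + 56). The apparent success rate is p = d × 0.35 + (1 − d) × q, where q is the average of S at the scan that counts.

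For L = 122 and lag 0 to 14:
- Share of late scans: 4/14 = 29%.
- Mean S over on-time scans (days 112 to 122) is 0.366. Mean S at the first scan for the late group (days 66 to 70) is 0.557.
- q = 0.714 × 0.366 + 0.286 × 0.557 = 0.420.

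| d | p | P(17 or more of 37) |
|---|---|---|
| 0.90 | 0.357 | 0.13 |
| 0.75 | 0.368 | 0.16 |
| 0.50 | 0.385 | 0.22 |

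If all start within 7 days, no scan is late, q = 0.370, and the three probabilities are 0.12, 0.12 and 0.14. This small excess over 0.112 arises because those scans fall a few days before day 122, not because any is late.

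**Sensitivity case, L = 112.** With lag 0 to 14, essentially every second scan is late. At d = 0.75, p = 0.401 and the probability is 0.29. At d = 0.50, p = 0.452 and it is 0.53.

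**Scoring on the cycle-4 scan instead** (uniform over days 112 to 126). If 35% and 55% refer to day 122, the mean success rates are 0.359 and 0.558, and 17/37 has alpha 0.14 and power 0.92. If they refer to day 112, the rates are 0.328 and 0.530, giving 0.07 and 0.85.

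**The case against.** **Existing safeguards.** Death is an event (16.52). Footnote 2 says "Tumor assessment should be performed at any time during the treatment cycle that disease progression is clinically suspected". Section 11.45 records symptomatic deterioration as PD. These stand and reduce the effect, but they do not reach silent progression, and the triggered scan is tied to a treatment cycle.

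**Usual practice.** Dating progression at documentation is normal for PFS time. That is correct; the gap lies in a yes/no landmark with no scan attached.

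**Alpha is not wrong.** Success is defined by documentation and the null hypothesis concerns that proportion, so 0.11 holds for the endpoint as written. A reader might take 0.16 or 0.22 to be the trial's real false-positive rate. The documents do not support that. Those values appear only if 35% is treated as a scan-free rate, whereas 16.41 reads it from a published PFS curve with its own scan lag.

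**16.13 does not fix the landmark.** A reader might infer day 112 from "16 weeks (4 months to evaluate the primary endpoint", or day 120 from "120 weeks (about 28 months". The paragraph uses a planning shorthand of 4 weeks per month throughout: 35 patients at 2 a month is 17.5 months, written as 70 weeks. Also, 120 weeks is 840/30.4375 = 27.6 months, so 28 is a rounding. Day 120 has no basis, and day 112 is at most a sensitivity case.

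**Early analysis is not licensed.** One might read 16.13 as allowing the final analysis before the last scan. It says analysis can begin "as soon as the last patient has been observed for 4 months and data have been submitted", so data must be in. The Analysis Plan paragraph after 16.43 refers to data maturity, and 16.6 requires at least 4 months of follow-up.

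**Conclusion.** The point holds as a defect in the endpoint rule. Section 16.31 counts elapsed time without recorded PD as success, requires no scan, and sets a landmark that the cycle-based second scan straddles. The Kaplan-Meier estimate in 16.512 does not cover late or missed scans. The sample size, alpha and power are correctly calculated for the endpoint as defined.

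The size is not known. On the calendar-month reading, the illustration runs from about 0.12 (prompt starts) to 0.22 (lags up to 14 days, half of progressions counted at once), against 0.11. It rests on the assumed exponential curve, lag distribution and detection share, and on reading 6.36 as at most 14 days. Holds would add to it. So would unscanned off-treatment patients, whose number the documents do not allow one to estimate. It would be too strong to say that the trial is biased toward a positive result against its benchmark, since the net direction cannot be determined. The rule should be fixed before data are analysed, because otherwise the landmark day is left to be chosen afterwards. Confidence is high on the missing text and low on the magnitude.

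**What to change.** 1. In 16.31, state the landmark in days. Score success on the second assessment already scheduled (post-cycle-4, about week 16), within a stated window that contains it: nominally days 112 to 126 plus an allowance for holds. PD at or before that scan, or death before it, is failure.
2. State that 35% and 55% refer to that day, and restate alpha and power if they do not. With scoring on the cycle-4 scan and the rates set for day 122, 17/37 gives about 0.14 and 0.92.
3. Reconcile 4.0, 11.1 and 18.0 on whether the 8-weekly re-evaluation applies to patients who stop treatment without PD.
4. Report 17/37 with patients lacking that assessment counted as non-successes, as a sensitivity analysis. It should not be the primary rule: if 5% or 10% of true successes lack the scan, the success rate at the alternative falls to 0.55 × 0.95 = 0.5225 or 0.55 × 0.90 = 0.495, and power to 0.82 or 0.72.

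The cost is wording. Patients on treatment need no extra scan; those off treatment need one only if item 3 confirms that 11.1 covers them. The downsides are a slightly lower apparent success rate, some patients scored a few days after the landmark (possibly stricter than the benchmark), and up to about two weeks' wait for the last scan.
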